## **7.4 Assuring Subject Compliance**

Most acalabrutinib doses will be taken by the subjects at home. Therefore, subjects will receive an acalabrutinib drug diary to record the specific time each dose was taken and to record reasons for any missed doses. Subject compliance with acalabrutinib dosing will be assessed at every visit and recorded in the eCRF. The subject will be instructed to bring the diary and any remaining tablets to the clinic at his/her next visit. The study staff will review the diary and ask the subject if all the tablets were administered. Any remaining or returned tablets will be counted and documented. Returned tablets must not be redispensed to another subject. The investigational products should only be used as directed in this protocol and as detailed in the pharmacy manual and handling instructions.

The study personnel at the investigational site will account for all drugs dispensed and for appropriate destruction or return of unused drugs to the sponsor or designee. All study supplies and associated documentation will be regularly reviewed and verified by the Site Monitor before destruction or return to the sponsor or designee. Certificates of delivery and destruction/return should be signed and copies must be retained by the sponsor.

## **7.5 Toxicity of Study Drug and Study Regimen**

### **7.5.1 Precautions and Risks Associated with Acalabrutinib**

#### **7.5.1.1 Hemorrhage**

Hemorrhagic events, including central nervous system, respiratory, and gastrointestinal hemorrhages, have been reported in clinical trials with acalabrutinib. Some of these bleeding events resulted in fatal outcomes.

The mechanism for hemorrhage is not well understood. Subjects receiving antiplatelet or anticoagulant therapies may be at increased risk of hemorrhage and should be monitored for signs of bleeding. Consider the benefit-risk of withholding acalabrutinib for at least 3 days pre- and post-surgery. Subjects with haemorrhage should be managed per institutional guidelines with supportive care and diagnostic evaluations as clinically indicated.

#### **7.5.1.2 Infection**

Serious infections, including fatal events, have been reported in clinical studies with acalabrutinib. The most frequently reported Grade 3 or 4 infection was pneumonia. Across the acalabrutinib clinical development program (including subjects treated with acalabrutinib in combination with other drugs), cases of HBV reactivation (resulting in liver failure and death in 1 case) and cases of progressive multifocal leukoencephalopathy (PML) have occurred in subjects with hematologic malignancies.

Subjects should be monitored for signs and symptoms of infections and treated as medically appropriate. Subjects with infection events should be managed according to institutional guidelines with maximal supportive care and diagnostic evaluations as clinically indicated.

#### **7.5.1.3 Cytopenias**

Treatment-emergent Grade 3 or 4 cytopenias including neutropenia, anemia, and thrombocytopenia have occurred in clinical studies with acalabrutinib. Monitor blood counts as medically appropriate.

#### **7.5.1.4 Second Primary Malignancies**

Events of second primary malignancies, including non-skin carcinomas, have been reported in clinical studies with acalabrutinib. The most frequently reported second primary malignancy was skin cancer.

Subjects with a second primary malignancy should be managed according to institutional guidelines with maximal supportive and therapeutic care and diagnostic evaluations as clinically indicated.

#### **7.5.1.5 Atrial Fibrillation**

Events of atrial fibrillation/flutter have been reported in clinical studies with acalabrutinib, particularly in subjects with cardiac risk factors, hypertension, diabetes mellitus, acute infections, and a previous history of atrial fibrillation. The mechanism for atrial fibrillation is not well understood.

Subjects with atrial fibrillation should be managed per institutional guidelines with supportive care and diagnostic evaluations as clinically indicated.

#### **7.5.1.6 Overdose**

Clinical information relevant to overdose is not available. For results from nonclinical overdose studies in rats and dogs, please refer to the IB.

In the event of subject ingestion of more than the recommended acalabrutinib dosage, the subject should be observed for any symptomatic side effects, and vital signs and biochemical and hematologic parameters should be followed closely (consistent with the protocol or more frequently, as needed). Appropriate supportive management to mitigate adverse effects should be initiated. If the overdose ingestion of acalabrutinib is recent and substantial, and if there are no medical contraindications, use of gastric lavage or induction of emesis may be considered.

## 8. DOSE MODIFICATIONS

If toxicity occurs, the toxicity will be graded using the NCI CTCAE Version 5, and appropriate supportive care treatment will be administered to decrease the signs and symptoms thereof. Dose adjustments will be based on the organ system exhibiting the greatest degree of toxicity.

### 8.1 Criteria and Procedures for Dose Interruptions and Adjustments of Acalabrutinib

Subjects should be followed closely for AEs or laboratory abnormalities that might indicate acalabrutinib-related toxicity. If a subject experiences a treatment-related toxicity or other intolerable AE during the course of therapy, then acalabrutinib should be withheld, as necessary, until the AE resolves or stabilizes to an acceptable degree.

Dose modifications for the following TEAEs are provided in Table 1.

- Grade 4 neutropenia (<500/ $\mu$ L) for >7 days (neutrophil growth factors are permitted per ASCO guidelines [Smith et al 2006, Smith et al 2015] and use must be recorded on the eCRF)
- Grade 3 thrombocytopenia (<50,000/ $\mu$ L) in the presence of significant bleeding.
- Grade 4 thrombocytopenia (<25,000/ $\mu$ L)
- Grade 3 or 4 nausea, vomiting, or diarrhea, if persistent despite optimal antiemetic and/or anti-diarrheal therapy
- Any other Grade 4 AE or unmanageable Grade 3 AE

**Table 1 Acalabrutinib Dose Reduction Options**

| Starting Dose | 1 st Dose Reduction | 2 nd Dose Reduction |
|---------------|--------------------------------|--------------------------------|
| 129 mg BID    | 129 mg QD                      | discontinue                    |

Temporarily withholding acalabrutinib for as little as 7 days can cause a transient worsening of disease and/or of constitutional symptoms. Transient worsening of disease during temporary interruption of study therapy (e.g. for drug-related toxicity, surgery, or intercurrent illness) may not indicate PD. In such circumstances, and if medically appropriate, following discussion with the Medical Monitor, subjects may resume therapy and relevant clinical, laboratory, and/or radiologic assessments should be done to document whether lymphoma control can be maintained or whether actual PD has occurred.

As appropriate, certain laboratory abnormalities may warrant more frequent monitoring (i.e., once per week) until abnormalities have recovered to Grade  $\leq 1$ . If acalabrutinib is reduced for apparent treatment-related toxicity, the dose need not be re-escalated, even if there is minimal or

no toxicity with the reduced dose. However, if the subject tolerates a reduced dose of acalabrutinib for  $\geq 4$  weeks then the dose may be increased to the next higher dose level, at the discretion of the PI. Such re-escalation may be particularly warranted if further evaluation reveals that the AE that led to the dose reduction was not treatment-related. The maximum dose of acalabrutinib is 129 mg BID.

Treatment with acalabrutinib should be withheld for any unmanageable, potentially study drug-related toxicity that is Grade  $\geq 3$  in severity. Any other clinically important events where dose delays may be considered appropriate must be discussed with the PI.

## **8.2 Dose Modifications for Hematologic Toxicities**

If the acalabrutinib dose should be reduced and the subject is receiving acalabrutinib 129 mg QD, acalabrutinib should be discontinued. Refer to Table 2 for dose modifications due to hematologic toxicities.

**Table 2 Dose Modifications for Hematologic Toxicities**

| NCI CTCAE Grade  | Acalabrutinib Action   |
|--|--|
| Febrile neutropenia Grade 3 or 4  | Withhold acalabrutinib until infection is resolved, antibiotics no longer required and ANC Grade $\leq 2$ or baseline. Then, restart acalabrutinib at the same dose.                                     |
| 2nd episode: febrile neutropenia Grade 3 or 4   | Withhold acalabrutinib until infection is resolved, antibiotics no longer required and ANC Grade $\leq 2$ or baseline. Then, restart acalabrutinib with 1 level dose reduction or discontinue (Table 1). |
| 3rd episode: febrile neutropenia Grade 3 or 4   | Discontinue acalabrutinib  |
|  |  |
| Neutrophil count decrease Grade 4 lasting $> 7$ days despite growth factor support                      | Withhold acalabrutinib until Grade $\leq 2$ or baseline. Then, restart acalabrutinib at the same dose.   |
| 2nd episode: neutrophil count decrease Grade 4 lasting $> 7$ days despite growth factor support         | Withhold acalabrutinib until Grade $\leq 2$ or baseline. Then, restart acalabrutinib with 1 level dose reduction or discontinue (Table 1).   |
| 3rd episode: neutrophil count decrease Grade 4 lasting $> 7$ days despite growth factor support         | Discontinue acalabrutinib  |
|  |  |
| Platelet count decrease Grade 4 without bleeding requiring blood or platelet transfusion                | Withhold acalabrutinib until Grade $\leq 2$ or baseline. Then, restart acalabrutinib at the same dose (Table 1).   |
| 2nd episode: platelet count decrease Grade 4 without bleeding requiring blood or platelet transfusion   | Withhold acalabrutinib until Grade $\leq 2$ or baseline. Then, restart acalabrutinib with 1 level dose reduction or discontinue (Table 1).   |
| 3rd episode: platelet count decrease Grade 4 without bleeding requiring blood or platelet transfusion   | Discontinue acalabrutinib  |
|  |  |
| Platelet count decrease Grade 3 or 4 with bleeding requiring blood or platelet transfusion              | Withhold acalabrutinib until Grade $\leq 2$ or baseline. Then, restart acalabrutinib with 1 level dose reduction or discontinue (Table 1).   |
| 2nd episode: platelet count decrease Grade 3 or 4 with bleeding requiring blood or platelet transfusion | Discontinue acalabrutinib  |

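### Section 8.1 and Table 2 set different triggers for Grade 3 thrombocytopenia with bleeding and for prolonged Grade 4 neutropenia, and no text says which governs

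*Combined protocol and SAP*

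**What the plan says.** Section 8.1 gives a list of events under the sentence "Dose modifications for the following TEAEs are provided in Table 1". Table 1 is the dose ladder: starting dose, one reduction, then discontinuation. The hematologic bullets are:

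- Grade 4 neutropenia (below 500/µL) for more than 7 days, with the remark that "neutrophil growth factors are permitted per ASCO guidelines";
- Grade 3 thrombocytopenia (below 50,000/µL) "in the presence of significant bleeding";
- Grade 4 thrombocytopenia (below 25,000/µL).

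The list ends with a catch-all: "Any other Grade 4 AE or unmanageable Grade 3 AE". Ahead of the list, for a treatment-related or otherwise intolerable event, 8.1 says "then acalabrutinib should be withheld, as necessary, until the AE resolves or stabilizes to an acceptable degree". The section closes with a further hold for unmanageable, potentially drug-related toxicity of Grade 3 or higher.

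Section 8.2 then says "Refer to Table 2 for dose modifications due to hematologic toxicities". For Grade 3 platelets, the Table 2 rows (first and second episode) are limited to "Grade 3 or 4 with bleeding requiring blood or platelet transfusion". The prolonged-neutropenia rows add the condition that the count stayed at Grade 4 despite growth factor. Table 2 also names Grade 3 or 4 febrile neutropenia, which the 8.1 list does not.

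**The concern.** Both lists are operative text in the current protocol, and both are specific: each gives grades and, where relevant, a duration or a bleeding qualifier. For two events the qualifiers differ. A site working from 8.1 and a site working from Table 2 can then reach different conclusions about whether the same event calls for a listed dose action.

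This matters because of the drug and the population. Section 7.5.1.1 says of hemorrhage with acalabrutinib: "Some of these bleeding events resulted in fatal outcomes". Section 3.2 admits post-transplant patients with platelets from 75,000/mm³ and neutrophils from 1,000/mm³. Table 2 also escalates by episode number, so whether an event meets the trigger decides whether it counts as an episode when the next one occurs.

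**Working it through.** The plan states no figure for this point and no power or sample-size calculation bears on it. The check sets the triggers of 8.1 beside the rows of Table 2.

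| Event | Named in 8.1 list? | Row in Table 2? | Result |
|---|---|---|---|
| Grade 3 platelets, no bleeding | No | No | Agree |
| Grade 3 platelets, significant bleeding, no transfusion needed | Yes | No | **Differ** |
| Grade 3 platelets, significant bleeding, transfusion needed | Yes | Yes | Agree |
| Grade 3 platelets, transfused bleeding not judged significant | No | Yes | Differ, depending on an undefined word |
| Grade 4 platelets | Yes | Yes, on the natural reading | Agree on trigger |
| Grade 4 neutropenia over 7 days, growth factor given | Yes | Yes | Agree on trigger |
| Grade 4 neutropenia over 7 days, no growth factor given | Yes | No | **Differ** |
| Grade 3 febrile neutropenia, manageable | Not named | Yes | 8.1 is silent |

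*Grade 3 platelets.* Section 8.1 does not mention transfusion; Table 2 makes it the condition. Neither passage says when bleeding is significant.

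*Grade 4 platelets.* The agreement assumes that the Table 2 row for Grade 4 without bleeding means without bleeding of the transfusion-requiring kind. If it means no bleeding but a transfusion required, Grade 4 platelets without transfusion also lack a row.

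*Prolonged neutropenia.* Section 8.1 permits growth factor but does not make its failure a condition; Table 2 does. Section 5.2.1 leaves growth factor use to institutional policy and guidelines, so with approximately 10 sites the same neutrophil course can meet the Table 2 condition at one site and not at another.

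*Precedence.* Section 8.1 sends its list to Table 1. Section 8.2 sends hematologic toxicity to Table 2. Neither sentence refers to the other list.

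*Size.* The nearest rates are those in Section 1.5 for 124 patients with relapsed mantle cell lymphoma: Grade 3 or higher neutropenia 10.5% and thrombocytopenia 4.0%. If these carried over to 50 patients, they would give 50 × 0.105 = 5.25 and 50 × 0.040 = 2.0 patients. These figures count the parent events in a different population. They do not measure the differing cells, which need further conditions (Grade 4 beyond 7 days without growth factor; Grade 3 with a significant, untransfused bleed). The documents give no fraction for either cell.

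**The case against.** The strongest reply is that the routing is clear enough: 8.1 is general, 8.2 is the specific hematologic instruction, and Table 1 is only a ladder that Table 2 itself cites. That reading is reasonable, but it is not stated. The 8.1 bullets are too specific to be set aside as general remarks.

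A second reply is that a patient missing from Table 2 is not left without action. This stands. The general hold sentences in 8.1 apply to intolerable or treatment-related events, and other clinically important events go to the principal investigator. A bleed might also be graded in its own right as a Grade 3 non-hematologic event, for which Table 3 withholds drug at first occurrence. These routes limit the consequence but do not remove the mismatch, because a hold by judgment is a different instruction from a listed modification.

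A reader might also infer more than the documents support:

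- *That any bleeding patient is treated differently by the two lists.* The firm conflict is one cell, Grade 3 platelets with significant, untransfused bleeding. Significant bleeding that needs transfusion is covered by both lists, and so are Grade 4 platelets on the natural reading.
- *That the lists contradict each other on febrile neutropenia.* Section 8.1 does not name it and does not say to continue drug. Table 2 names it, and 8.2 sends the reader there. This is mostly silence filled by the specific table.
- *That the mismatch moves the safety rule in Section 3.5.* That rule asks whether 30% or more are unable to stay on drug because of adverse events (30% of 20 = 6 patients); it does not count dose reductions. For a patient still on the starting dose, neither list mandates discontinuation at first occurrence in either differing cell. Section 10.4.3 likewise plans a summary of events leading to discontinuation, not of reductions. Any effect would be indirect, through later episodes, and cannot be sized.

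**Conclusion.** The point holds as an internal inconsistency in two named triggers: the bleeding qualifier for Grade 3 thrombocytopenia, and the growth-factor condition for Grade 4 neutropenia beyond 7 days. The naming of febrile neutropenia in only one place is a lesser matter of completeness. Following the plan as written can lead to different dose actions for the same event, and the text does not settle which applies.

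The number of patients involved is probably small. That is a judgment: it rests on how narrow the two cells are, and the documents do not give the fraction. The sample size and the primary analysis at 2 years post-transplant are not affected. The reason to act is consistent safety management across sites. The conclusion assumes that both the 8.1 list and Table 2 are meant to be followed, and it takes no position on which clinical rule is right.

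**What to change.** The sponsor's medical team should reconcile the hematologic triggers in 8.1 with Table 2 so that each event has one trigger stated in the same terms wherever it appears. If significant bleeding is kept as a term, it should be defined. One sentence in 8.1 or 8.2 should state which passage governs hematologic events. The same edit can settle how febrile neutropenia is cross-referenced and how the Grade 4 platelet row is to be read. Removing either list would itself select or drop a clinical rule, so that choice also belongs to the medical team.

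The cost is wording in 8.1, 8.2 and Table 2 at the next amendment, with a memo to sites. No visits, tests or analyses are added.

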### **8.3 Dose Modifications for Non-hematologic Toxicities**

In case of Grade 4 treatment-related non-hematologic toxicity, discontinue acalabrutinib.

Grade 3 toxicities require dose modifications, temporary treatment interruptions or discontinuation of acalabrutinib (Table 3).

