### **3.5 Study-wide Stopping Rules**

If after 20 patients have been accrued to the study, 30% or more are unable to stay on acalabrutinib due to AEs, enrollment will be stopped, and a comprehensive review of safety will be performed by the study chair, primary investigators, and representatives of Acerta Pharma/AstraZeneca.

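### Sections 8.1 and 8.3 give different actions for a treatment-related Grade 4 non-hematologic toxicity, and no text says which governs

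*Combined protocol and SAP*

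**What the plan says.** **Section 8.1** opens its list of triggering events with "Dose modifications for the following TEAEs are provided in Table 1". Two entries reach Grade 4 non-hematologic events:

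- The gastrointestinal entry reads "Grade 3 or 4 nausea, vomiting, or diarrhea, if persistent despite optimal antiemetic and/or anti-diarrheal therapy".
- The catch-all entry that closes the list reads "Any other Grade 4 AE or unmanageable Grade 3 AE".

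Neither entry depends on relatedness or on the number of the episode. Elsewhere 8.1 says to withhold drug until recovery or stabilization, and it repeats the withholding instruction for unmanageable, possibly drug-related toxicity of Grade 3 or above.

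**Table 1** has three positions: 129 mg BID at the start, 129 mg QD as the first reduction, and discontinuation as the second.

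**Section 8.3** states: "In case of Grade 4 treatment-related non-hematologic toxicity, discontinue acalabrutinib". It sends Grade 3 non-hematologic events to Table 3.

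**Section 8.2** refers hematologic toxicities to Table 2, although the 8.1 list also includes "Grade 4 neutropenia" lasting over 7 days and Grade 4 thrombocytopenia. For platelets, 8.1 qualifies Grade 3 by "in the presence of significant bleeding", while the corresponding Table 2 row reads "Grade 3 or 4 with bleeding requiring blood or platelet transfusion".

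**Section 3.5** stops enrollment and starts a safety review if, once 20 patients have been accrued, "30% or more are unable to stay on acalabrutinib due to AEs". **Section 10.4.3** plans a summary of AEs that lead to stopping treatment.

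**The concern.** A first treatment-related Grade 4 non-hematologic event in a patient on 129 mg BID meets both instructions. One leaves a route to continue at a lower dose; the other ends treatment. About 10 sites are planned, and two of them could treat the same serious event differently without either departing from the protocol.

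The statistical consequence follows from the clinical one. A patient who is reduced remains on drug. A patient who is discontinued enters the table of AE-related discontinuations and is a natural candidate for the Section 3.5 count. Both safety outputs would then partly reflect which page a site consulted.

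**Working it through.** **Step 1: compare the instructions by event.** The Table 1 column takes the sentence in 8.1 at face value and assumes the patient is on the starting dose at the first event.

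| Event | 8.1 with Table 1 | 8.3, Table 2 or Table 3 | Patient on or off drug? |
|---|---|---|---|
| Related Grade 4 non-hematologic, first (including persistent Grade 4 GI) | Reduce to QD | 8.3: discontinue | Differs |
| Grade 4 neutropenia over 7 days, or Grade 4 platelets without bleeding that needs transfusion, first | Reduce to QD | Table 2: resume at unchanged dose | Same (on drug) |
| The same hematologic events, second | Discontinue | Table 2: reduce one level or discontinue | Can differ |
| Platelets, Grade 3 or 4, with bleeding that needs transfusion, first | Reduce to QD | Table 2: reduce one level or discontinue | Compatible |
| Persistent Grade 3 GI, first | Reduce to QD | Table 3: resume at unchanged dose | Same (on drug) |

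Only the first row is a direct clash that decides at once whether the patient stays on drug. It is limited to patients still on 129 mg BID: for someone already on QD, the next Table 1 position is discontinuation, which agrees with 8.3.

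**Step 2: look for a precedence rule.** The opening of Section 8 bases adjustments on the organ system with the worst toxicity, which does not choose between 8.1 and 8.3. Section 8.2 names Table 2 for hematologic events. No corresponding sentence says that 8.3 overrides 8.1 for non-hematologic events.

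**Step 3: size of the effect on the stopping rule.** The documents give a 30% limit and a start at 20 accrued patients. They state no operating characteristics, so there is no plan figure to reproduce. If the denominator is 20:

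- Threshold: 0.30 × 20 = 6 patients.
- One patient classified differently: 1/20 = 5 percentage points.
- Two such patients can move 4/20 (20%) to 6/20 (30%).

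**Step 4: illustration under assumed rates.** Let d be the share off drug for AEs under every reading, and g the extra share discontinued only under 8.3. Neither is in the documents. With independent patients and a single look at 20, the chance of meeting the rule is P(X ≥ 6), where X is binomial with n = 20 and p = d under 8.1 or p = d + g under 8.3.

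| p | 5% | 10% | 15% | 20% | 25% | 30% | 35% |
|---|---|---|---|---|---|---|---|
| P(X ≥ 6) | 0.03% | 1.1% | 6.7% | 19.6% | 38.3% | 58.4% | 75.5% |

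With d = 10%, the 8.1 reading gives 1.1%. The 8.3 reading gives 6.7%, 19.6% or 38.3% for g = 5%, 10% or 15%. With d = 5%, the figures are 0.03% against 1.1%, 6.7% or 19.6%. With d = 20%, they are 19.6% against 38.3%, 58.4% or 75.5%.

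**The case against.** The strongest defense is that Table 1 only lists the available dose levels, while 8.2, 8.3 and Tables 2 and 3 set the action. Its title speaks of reduction options, and Tables 2 and 3 cite it in places even where the dose is unchanged. Together with the referral in 8.2 to Table 2, this largely answers the hematologic mismatch. It does not settle the non-hematologic one: 8.1 says the modifications for its listed events are in Table 1, and 8.3 offers no modification at Grade 4, only discontinuation.

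A second defense is scope: 8.1 covers treatment-emergent events of any cause, 8.3 only related ones. This is correct and narrows the clash to the related subset. It does not remove it, because 8.1 also addresses drug-related toxicity directly and prescribes withholding, with no compulsory stop at Grade 4. Grade 3 gastrointestinal events fall outside the discontinuation sentence in 8.3.

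The bleeding wording is a minor point. Transfusion need can be read as the working definition of significant bleeding. Still, a Grade 3 platelet decrease with significant bleeding but no transfusion triggers 8.1 and has no row in Table 2.

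A reader might infer two stronger claims that the documents do not support:

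- **That the contradiction feeds PFS censoring.** Sections 9.1 and 10.4.2 do not censor for stopping study drug. They censor for subsequent therapy and, in 10.4.2, for leaving the study or loss to follow-up; Section 5 continues PFS follow-up to 5 years post-BMT. Any link runs only through later therapy, which Section 6.4.5 permits after discontinuation.
- **That every mismatch moves the stopping count.** First hematologic episodes do not, since the patient stays on drug under either reading.

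**Conclusion.** The contradiction between 8.1 with Table 1 and 8.3 is real for a treatment-related Grade 4 non-hematologic toxicity, including persistent Grade 4 nausea, vomiting or diarrhea, in a patient on the starting dose. It bears on patient safety and should be corrected. Confidence is high on this clash. The hematologic and bleeding-wording differences are secondary drafting inconsistencies.

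The numerical effect is illustrative only. The 5 points per patient assumes a denominator of 20, and Section 3.5 defines neither the denominator nor what being unable to stay on drug means. The probabilities rest on assumed rates. The documents do not show that the count would in fact cross 30%, and crossing it stops enrollment for a safety review; it is not a test of the primary endpoint.

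**What to change.** Reconcile Section 8.1, Table 1, Table 2, Section 8.3 and Table 3 so that each toxicity and grade has one trigger wording and one action, or add a sentence stating which section governs when they differ. Use the same bleeding criterion for platelets in 8.1 and Table 2. Which action and which trigger are right is for the sponsor's clinical team.

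The cost is an amendment to Section 8 and a short notice to sites. If patients have already been treated, a listing of related Grade 4 non-hematologic events with the action taken, which Section 11.1.6.1 already has sites record, would show whether handling has differed. No change to the sample size or the PFS analysis follows from this point.

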#### **10.4.3 Safety Analysis**

Safety will be assessed through the analysis of the reported incidence of treatment-emergent AEs. Treatment-emergent AEs are those with an onset on or after the initiation of therapy, and will be graded according to NCI CTCAE Version 5.0. A copy of the CTCAE scoring system may be downloaded from:

[https://ctep.cancer.gov/protocolDevelopment/electronic\\_applications/docs/CTCAE\\_v5\\_Quick\\_Reference\\_8.5x11.pdf](https://ctep.cancer.gov/protocolDevelopment/electronic_applications/docs/CTCAE_v5_Quick_Reference_8.5x11.pdf).

The AEs will be coded using the Medical Dictionary for Regulatory Activities (MedDRA) and summarized using system organ class and preferred term for all patients in the Safety Analysis Set. In addition, summaries of SAEs, AEs leading to treatment discontinuation, AEs by maximum NCI CTCAE grade, and AEs related to the study drug will also be presented.

Other safety endpoints including laboratory results, vital signs, ECG findings, and other protocol-specified tests will be listed and/or summarized for all patients in the Safety Analysis Set.

Concomitant medications will be coded using the WHO Drug Dictionary and they will be listed and summarized.

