### **11.1.6 Recording and Reporting of Adverse Events**

#### **11.1.6.1 Recording of Adverse Events**

All AEs of any patient during the course of the research study will be recorded in the eCRF, and the Investigator will give his or her opinion as to the relationship of the AE to the study drug (e.g., whether the event is related or unrelated to study drug administration).

All AEs should be documented. A description of the event, including its date of onset and resolution, whether it constitutes an SAE or not, any action taken (e.g., changes to study drug), and outcome should be provided along with the Investigator’s assessment of causality (e.g., the relationship to the study drug). For an AE to be a suspected TEAE there should be at least a reasonable possibility of a causal relationship between the protocol treatment and the AE. Adverse events will be graded according to the NCI CTCAE Version 5.0, and changes will be documented.

If the AE is serious, it should be reported immediately to the Innovations Safety Department. Other untoward events occurring in the framework of a clinical study are to be recorded as AEs (e.g., AEs that occur prior to assignment of the study drug that are related to a protocol-mandated intervention, including invasive procedures such as biopsies, medication washout, or no treatment run-in).

Any clinically significant signs and symptoms, abnormal test findings, changes in physical examination, hypersensitivity, and other measurements that occur will be reported as AEs and collected on the relevant eCRF screen.

Test findings will be reported as an AE if: the test result requires an adjustment in the study drug(s) or discontinuation of treatment; test findings require additional testing or surgical intervention; a test result or finding is associated with accompanying symptoms; and/or a test result is considered to be an AE by the Investigator.

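### For a patient on 129 mg BID with a Grade 4 treatment-related non-hematologic toxicity, Section 8.3 says stop while Section 8.1 and Table 1 offer 129 mg QD, and no text says which governs

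*Combined protocol and SAP*

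**What the plan says.** Three places in the current protocol text bear on this event.

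- **Section 8.3**: "In case of Grade 4 treatment-related non-hematologic toxicity, discontinue acalabrutinib". No exception or condition is attached.
- **Section 8.1**: "Dose modifications for the following TEAEs are provided in Table 1". The list that follows has three hematologic entries and then two that reach non-hematologic events: "Grade 3 or 4 nausea, vomiting, or diarrhea, if persistent despite optimal antiemetic and/or anti-diarrheal therapy" and "Any other Grade 4 AE or unmanageable Grade 3 AE".
- **Table 1**, titled "Acalabrutinib Dose Reduction Options": the starting dose is 129 mg BID, the first reduction is 129 mg QD, and the second step is to discontinue. The text below the table, still in Section 8.1, says that if a reduced dose is tolerated for at least 4 weeks, "then the dose may be increased to the next higher dose level, at the discretion of the PI".

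Section 3.5 holds the only study-wide stopping rule. Once 20 patients have been accrued, enrollment stops and a safety review follows if AEs have kept 30% or more from remaining on the drug.

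**The concern.** The two sections give incompatible instructions for one event. Under Section 8.3 the drug is stopped for good. Under Section 8.1 and Table 1 the patient can restart at half the daily dose and later return to the full dose. With approximately 10 sites and no precedence sentence, sites can follow the protocol and still act differently.

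Two things are at stake. The first is patient safety: re-exposure after a Grade 4 drug-related toxicity is ruled out in one place and allowed in another. The second is the Section 3.5 trigger. A patient discontinued under Section 8.3 counts toward it. A patient kept on QD is still taking the drug and, on the natural reading, does not count.

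**Working it through.** The plan states no figure for this point, so the check is mainly a comparison of texts, with one piece of arithmetic.

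**Step 1. Do both rules reach the same event?** Take a patient on 129 mg BID with drug-related Grade 4 diarrhea that persists on optimal treatment.

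| Source | Does it apply? | Action |
|---|---|---|
| 8.3 | Yes: Grade 4, related, non-hematologic | Discontinue |
| 8.1, GI entry, with Table 1 | Yes: Grade 4 diarrhea is named | 129 mg QD first |
| 8.1, text below Table 1 | Yes, once on QD for at least 4 weeks | May return to 129 mg BID |

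For any other drug-related Grade 4 non-hematologic event, the catch-all entry in Section 8.1 gives the same result.

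**Step 2. Is the Section 8.1 list limited to unrelated events?** No. Section 8.1 opens by naming treatment-related toxicity alongside other intolerable AEs. Its list is of TEAEs, and the protocol describes these in two ways. Section 10.4.3 uses onset alone: "Treatment-emergent AEs are those with an onset on or after the initiation of therapy". Section 11.1.6.1 brings in causality: "For an AE to be a suspected TEAE there should be at least a reasonable possibility of a causal relationship". A drug-related Grade 4 event that starts on treatment satisfies both.

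**Step 3. Which patients are affected?** Only those on BID with a related Grade 4 non-hematologic event. A patient already on QD reaches discontinuation under Table 1 as well. An unrelated Grade 4 non-hematologic event falls under Section 8.1 only.

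**Step 4. Effect on the Section 3.5 count.** The inputs, both from Section 3.5, are 20 patients and a 30% threshold.

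- Threshold count: 0.30 × 20 = 6 patients.
- Weight of one patient: 1/20 = 5 percentage points.
- Example: five patients have stopped for other AEs and one has a related Grade 4 non-hematologic event.
  - Under Section 8.3: (5 + 1)/20 = 6/20 = 30%, and enrollment stops.
  - Under Section 8.1 and Table 1: 5/20 = 25%, and enrollment continues.

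**Step 5. Can this be given a probability?** Not from the documents. That would need the rate of related Grade 4 non-hematologic events and the rate of stopping for other AEs in this post-transplant setting, and neither is given. The nearest figures are in Section 1.5, for relapsed or refractory disease: Grade 3 or higher diarrhea in 3.2%, and drug-related SAEs in 12.1%. The population differs, the diarrhea figure separates neither Grade 4 events nor related ones, and the SAE figure includes hematologic events.

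**The case against.** The strongest reply is that Table 1 is only a ladder of dose levels, with the action for each event coming from Sections 8.2 and 8.3. Table 2 supports this. Section 8.1 also sends Grade 4 neutropenia lasting more than 7 days to Table 1, yet Table 2 restarts the first episode at the same dose. A reader might infer that Section 8.1 makes QD mandatory as the first step for every listed event. That goes too far, because the same reading would put Section 8.1 at odds with Table 2. On the ladder reading, Section 8.3 supplies the action for related Grade 4 non-hematologic events, and the Grade 4 entries in Section 8.1 still have work to do for unrelated ones.

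This reading is plausible and may be what was intended, but the protocol does not state it. Section 8.1 says that the modifications for these events are in Table 1. It also does not fit the whole list: Table 2 is hematologic and Table 3 is Grade 3 only, so for unrelated Grade 4 non-hematologic events Section 8.1 with Table 1 is the only dose-modification rule. Nor does the principle that the specific rule prevails settle the matter, since for Grade 4 vomiting or diarrhea Section 8.1 is the text that names the event.

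A second reply is that the consequence is limited. This is correct. The Section 3.5 trigger leads to a halt in enrollment and a review. The PFS definition in Section 9.1 does not count stopping the drug as an event, so the definition of the primary endpoint is unaffected.

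**Conclusion.** Wrong as written. For a patient on 129 mg BID with a related Grade 4 non-hematologic toxicity, Section 8.3 requires discontinuation, Section 8.1 and Table 1 allow QD with later re-escalation, and nothing ranks them. This follows from the text alone.

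The effect on the stopping rule is one patient, or 5 percentage points at 20 patients, for each event handled differently. That is enough to move 6/20 to 5/20. It assumes that a patient on QD is not counted under Section 3.5, and that the patient has not later stopped for an AE by the time of the count.

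A reader might infer three further things that the documents do not support:

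- That the stopping rule is likely to miss a safety signal. No usable event rate is given, so any probability would rest on invented inputs.
- That Section 8.1 and Table 3 also conflict for Grade 3 events. Their wording differs, but no incompatible instruction has been shown.
- That management of Grade 3 liver toxicity is missing. Table 3 excludes liver dysfunction, but Section 5.2.1 points to Appendix H for emesis, diarrhea and nausea, and the Appendix H text available covers only PML and infections. It may be incomplete, so the absence cannot be charged to the plan.

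**What to change.** Add to Section 8.1, after the list of events:

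> *For Grade 4 treatment-related non-hematologic toxicity, including nausea, vomiting or diarrhea, Section 8.3 governs: discontinue acalabrutinib; Table 1 reduction and re-escalation do not apply. Table 1 gives dose levels; Tables 2 and 3 give the action for the events they list.*

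Leave the GI entry otherwise unchanged. Limiting it to Grade 3 would move unrelated Grade 4 GI events into the catch-all entry, where the requirement that they persist on optimal treatment no longer applies.

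The cost is a short wording amendment, with no change to sample size, visits or analysis. The downside is that patients with such an event lose the QD option, which Section 8.3 already denies them. The documents do not show which rule the sponsor intended. If QD is meant to stay available for some of these events, the exception has to be written into Section 8.3 instead. Either way, one rule should apply at every site.
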